Apathy, which is defined as the loss or reduction of interest and goal-directed behaviors, is the most common NPS in ADRD, with a 5-year prevalence over 70% in this population (7, 8). Apathy has been associated with greater functional impairment, greater caregiver burden, increased risk of institutionalization and higher costs (9, 10). Because of its prevalence and clinical meaning, apathy is an important target in the management of ADRD. Standard pharmacological approach for apathy in ADRD uses cholinesterase inhibitors such as donepezil, with evidence of either no or very small effectiveness (10, 11). The stimulant methylphenidate was also shown to be effective in reducing apathy in ADRD in open studies and two double-blind randomized controlled trials (12). However, the use of methylphenidate was associated not only with reduction in apathy but also with greater anxiety and weight loss (13). Another concern with the use of stimulants is their potential cardiovascular effects, a fact particularly relevant in older adults with multiple medical comorbidities (14). Studies investigating non-pharmacological strategies for apathy in ADRD, such as music, art therapy and psychomotor activity, have modest effects and only in patients in early stages of dementia (15). Therefore, there is a great need to develop effective and safe strategies for the treatment of apathy in ADRD.

Transcranial direct current stimulation (tDCS) is a relatively novel non-pharmacological method of neuromodulation that has been evaluated in several neuropsychiatric conditions, showing promising results in depression and negative symptoms (including apathy) of schizophrenia (16, 17). tDCS modulates brain activity through low-intensity electrical currents applied over the scalp, and has been associated with significant changes in network connectivity involving the prefrontal cortex and the cingulate cortex, regions implicated in the neural basis of apathy (18-20).

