We will carry out a randomized, experimenter- and participant-blinded trial comparing home-based active tDCS and home-based sham tDCS. Participants will be randomized 1:1 to either treatment condition. Half of the participants (n=20) will receive active (constant current intensity of 2mA), while half (n=20) will receive sham tDCS. No changes to the patient's standard care medication will be made. Participants will continue to receive standard treatment for their individual health problems. **Anode and cathode electrodes will be placed over the left and right dorsolateral prefrontal cortices, respectively, with the use of the Omni-Lateral-Electrode system.** Caregivers will set up and administer tDCS for participants with ADRD at home. tDCS will be applied for 30 min at an intensity of 2mA, with 30 s ramping up and down. The same procedure will be used for sham stimulation, but in this case, electric current will be applied only in the first 30s tDCS. All patients, caregivers and clinicians will be blinded to the type of stimulation delivered. We will use bi-hemispheric stimulation (anode F3/cathode F4) based on the facts that bilateral frontal circuits have been implicated in apathy, and bilateral stimulation may have wider effects on brain networks (18, 23, 26). The stimulation will last 30 min according to previous studies (17, 23, 27). According to our previous home-based tDCS protocols (28, 29), all sessions will be remotely supervised by trained research staff (RA), therefore, the sessions will run from Monday to Friday. The remote supervision of the sessions will be possible through video conferencing software (e.g., WebEx), and will ensure the use of proper technique and compliance to the study schedule, also monitoring any adverse events (Fig.1). The devices (tDCS & sham tDCS) will be programmed and cannot be tampered. Participants will be assessed at baseline,

[figure not shown]
[figure not shown]

Fig. 1 Illustrative image of home-based tDCS.

treatment day 14, treatment day 28, treatment day 42, and 6 weeks post-treatment (Fig. 2). The device will be returned in person at the end of the treatment (week 6).

Fig. 2 Proposed outline of the study.

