Inclusion criteria will be: (1) diagnosis of possible or probable ADRD according to the National Institute of Aging – Alzheimer’s Association diagnostic criteria (34); (2) mild or moderate dementia, **as defined by a MMSE score between 14 and 26** (35, 36); (3) clinically meaningful apathy for at least four weeks, clinically diagnosed according to 2018 Apathy Diagnostic Criteria (37) or defined as Neuropsychiatric Inventory (**NPI-Q**) apathy score equal or above 4 (i.e., severity of ‘moderate’ or greater **and caregiver distress ‘mild or greater’** (38-40); (4) stable doses of cholinesterase inhibitors, memantine and other psychotropic medications for at least three months.

Exclusion criteria will be: (1) unstable medical conditions; (2) history of epilepsy; (3) metallic objects in the brain; (4) diagnosis of major depression and/or a score higher than 18 on the Cornell Scale for Depression in Dementia (41).

Recruitment and Retention. Subjects will be recruited at the *UTHealth Geriatric Neuropsychiatry Clinic, the Harris County Psychiatric Center (HCPC)* ([name]) and the *UT Physicians Center for Healthy Aging* ([name]). As serious adverse effects and problems with the device use are not anticipated, it is expected a high retention rate. The remote supervision of the tDCS or tDCS sham daily sessions by trained research staff will contribute to the retention of subjects during the trial.

Training plan. Patients will be instructed on treatment at baseline, when they will receive the device. A trained research staff will instruct the participant's caregiver on how to handle the equipment. All sessions will be remotely supervised by trained research (RA) staff, who will be able to answer questions during the sessions and verify that the device is being used correctly.

Study Procedures

Feasibility measures will include recruitment rate (per month), randomization success, blind success, retention and attrition rates. Overall consent and completion rates will be evaluated via descriptive statistics. Generalized linear modeling (GLM) will evaluate treatment group differences in consent and completion rates. We expect that a high proportion of participants will consent to participate (> 80%) and complete the study (> 70%).

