The secondary clinical outcome measures will include: (1) total score on the Brief Dimensional Apathy Scale (bDAS) (43); (2) total score on the NPI-Q which evaluates 12 discrete NPS considering their severity and the related caregiver distress (38-40); (3) depressive symptoms as assessed by the Cornell Scale for Depression in Dementia (41); (4) cognition as evaluated by the Mini-Mental State Examination (MMSE), which includes memory, language, praxis and orientation tasks, yielding a global cognition score ranging 0 to 30, with higher scores indicating better performance (35).

Our hypothesis is that active tDCS group will demonstrate lower scores on the bDAS, NPI-Q and Cornell Scale for Depression, and higher scores on the MMSE at the end of treatment relative to sham tDCS. GLM will evaluate residual change in each outcome (in separate models) by modeling scores at the end of treatment as a function of treatment group, controlling for baseline.

Sociodemographic data (gender, age, marital status and education) will be collected at the baseline. Clinical (health history, use of medication and life habits) and anthropometric data will be collected at the baseline and after the treatment period. These data will be control variables for the study.

Table 1. Timetable for Collection of Data

Assessment	Baseline	Week 2	Week 4	Week 6	Week 12
Medical History Questionnaire	X				
MMSE	X			X	X
AES (primary outcome)	X	X	X	X	X
NPI-Q	X	X	X	X	X
bDAS	X	X	X	X	X
Cornell Scale for Depression	X			X	X
tDCS experience questionnaire		X	X	X	X
Side effects questionnaire		X	X	X	X

Data and Safety Monitoring

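### Medication use is meant to be recorded again after treatment, but Table 1 schedules no such record and no change would be dated, so the trial could not show whether psychotropic changes contributed to or masked the apathy result

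*Combined protocol and SAP*

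**What the plan says.** All references are to the combined protocol and SAP.

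- **Study Population, inclusion criterion 4:** "stable doses of cholinesterase inhibitors, memantine and other psychotropic medications for at least three months". This is an entry condition and does not extend past enrolment.
- **Study Design:** "No changes to the patient's standard care medication will be made", followed by "Participants will continue to receive standard treatment for their individual health problems". Neither sentence says who is bound, how adherence would be checked, or what happens to the data if a drug is changed.
- **Study Procedures, before Table 1:** "Clinical (health history, use of medication and life habits) and anthropometric data will be collected at the baseline and after the treatment period". The next sentence adds: "These data will be control variables for the study".
- **Table 1:** there is no medication row. The only history item, "Medical History Questionnaire", is marked at baseline and nowhere else. The AES is marked at baseline and weeks 2, 4, 6 and 12.
- **Background Information:** "methylphenidate was also shown to be effective in reducing apathy in ADRD". The same section reports little or no benefit from cholinesterase inhibitors.
- **Statistics:** sample characteristics related to both predictor and outcome are added as covariates. Nothing is said about medication changed after randomisation.

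**The concern.** The plan treats medication as relevant to apathy: it restricts it at entry and names it a control variable. A site working from Table 1 would nevertheless collect nothing on medication after baseline, so the analyst would lack data that Study Procedures relies on. Even if the text is followed, one later snapshot cannot tell whether a given AES score came before or after a drug change.

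At stake is the reading of the efficacy result. If more sham participants were started on a drug because apathy persisted, a real effect could be masked. If changes ran the other way, a drug effect could pass for a tDCS effect. Without dated records nobody could tell, and undated changes may not be reliably recoverable later.

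The sentence that medication and other clinical data will be control variables adds a second hazard: it lets a post-baseline medication variable enter the model as an ordinary covariate, although treatment may have influenced it.

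**Working it through.** **1. What each reading would record.** The AES has four post-baseline assessments (weeks 2, 4, 6, 12).

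| Reading | Medication records after baseline | What can be learned |
|---|---|---|
| Table 1 | 0 | No change is visible |
| Text, record at week 6 | 1 | Who differs from baseline at week 6; weeks 2 and 4 cannot be placed before or after the change; weeks 6 to 12 unobserved |
| Text, record at week 12 | 1 | Who differs at week 12; not even the week-6 score can be placed before or after the change |

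In no case is there a date, and a drug started and stopped between records is missed.

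**2. The plan's own power figure.** Inputs from Statistics: N = 40, alpha 0.05, Cohen's f = 0.45, power 80%.
- Noncentrality = f² × N = 0.2025 × 40 = 8.1.
- With 1 and 37 degrees of freedom, two-sided, power is 79.1%, which agrees with the stated 80%.
- For two equal arms d = 2f = 0.90 SD.

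**3. Changes equally common in both arms.** The documents give no rates or effects. Assume a proportion q = 10 to 30% change medication, with an effect of m = 0.3 to 0.8 SD.
- Diluted effect = 0.90 / √(1 + q(1 − q)m²).
- At q = 0.1, m = 0.3: 0.90 / √1.0081 = 0.896, power 78.8%.
- At q = 0.3, m = 0.8: 0.90 / √1.1344 = 0.845, power 74.0%.

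This is noise, not bias, and costs at most about 5 points of power.

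**4. Changes that differ by arm.** Assume rates 10 to 20 percentage points apart (2 to 4 more of 20 in one arm), all acting in one direction, with the same m.
- Smallest shift = 2/20 × 0.3 = 0.03 SD; largest = 4/20 × 0.8 = 0.16 SD.
- Relative to 0.90 SD: 0.03/0.90 = 3% and 0.16/0.90 = 18%.

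**5. Effect on the 0.75 posterior level.** Take the default prior as near-flat.
- SE = √(2/20) = 0.316 SD.
- The level is met at 0.674 × 0.316 = 0.213 SD.
- With no tDCS effect and a favourable shift s, the chance of meeting it is 1 − Φ(0.674 − s/0.316).
- s = 0: 25%. s = 0.03: 1 − Φ(0.579) = 28%. s = 0.16: 1 − Φ(0.168) = 43%.

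**6. Chance imbalance.** With 20 per arm and a common change rate of 10 to 30%, a difference of at least 3 participants in either direction has probability 18 to 39%. That is common, but it is part of the sampling variation that the SE in step 5 describes. It must not be counted again as bias.

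**The case against.** The strongest reply has four parts.

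*Table 1 does not contradict the text.* The documents never say that the history questionnaire records medication, and Table 1 is plainly not exhaustive: the sociodemographic and anthropometric data have no rows either. This stands. The fault is an omission from the schedule, but the omitted item is one the analysis expects to use.

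*The plan does address medication during the trial.* The Study Design sentences can be read together as usual care continuing unaltered. That is a fair reading, but the wording does not settle whether it restricts prescribing or only says that the study team will not intervene, and nothing checks it.

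*Blinded 1:1 randomisation protects the comparison.* This stands in full. A reader might infer that, without medication data, a tDCS effect cannot be separated from drug effects, or that chance imbalance biases the week-6 result. The documents do not support either. Patients, caregivers and clinicians are blinded, imbalance is within the SE, and if the text is followed, one snapshot would show who had changed by the time it was taken. A week 6 to 12 gap touches only the follow-up analyses.

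*The drug effect may be small.* A reader could assume 5 to 8 AES points per change. With an assumed SD of 7 that is 5/7 = 0.71 to 8/7 = 1.14 SD, about as large as the 0.90 SD the trial is powered for, and nothing in the documents supports it. The background's weak evidence for cholinesterase inhibitors points the other way for those drugs.

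Efficacy is also the secondary goal, which limits the stakes without removing them.

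**Conclusion.** The point holds as a gap in data collection that limits interpretation. The randomised week-6 comparison stands. What the trial could not show is whether medication changes driven by symptoms, or differing by arm, contributed to the AES difference or hid one. At most one of the four post-baseline AES assessments would be accompanied by a medication record, and none if Table 1 is followed.

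The numerical size is illustrative: 0.03 to 0.16 SD if change rates differ by 10 to 20 percentage points and the drug effect is 0.3 to 0.8 SD, all in one direction. That is modest against the frequentist target but more noticeable against the 0.75 posterior level, which the plan treats as its primary inferential focus. The documents offer no evidence that such a difference between arms will occur; the point is that it would go undetected. This is a worthwhile, inexpensive improvement.

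**What to change.** 1. Reconcile the medication sentence in Study Procedures with Table 1, and state which instrument records medication.
2. Add a Table 1 row for psychotropic medication (drug, dose, and start, stop or change date) at baseline and weeks 2, 4, 6 and 12, and tabulate changes by arm.
3. Keep all randomised participants and all their scores in the main analysis. Limit medication covariates to baseline values; do not enter post-baseline medication as an ordinary covariate.
4. Prespecify one supportive sensitivity analysis for AES scores recorded after a psychotropic change, labelled as conditioning on a post-randomisation event. It can show how far the result depends on those scores, but it cannot cleanly separate drug from device.
5. Clarify what the two Study Design sentences on medication mean and whom they bind. The clinical rule itself is for the investigators.

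Cost: one table row, a few minutes of caregiver time at assessments already scheduled, and one extra analysis.

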Given the clinical relevance of apathy in ADRD, the equivocal results of the therapeutic resources available to address it, and the emerging evidence of safety and efficacy of tDCS in ADRD, our proposal aims to test the feasibility, safety and efficacy of home-based tDCS for the treatment of apathy in ADRD. Home-based tDCS circumvents critical problems observed in previous trials (25), including the need of multiple visits to medical centers for tDCS application, allowing a more intensive application (e.g. 5 x per week) for prolonged periods.

Objectives

Objectives	Outcome Measures

Primary objective To assess feasibility, acceptability, and safety of providing tDCS to ADRD patients with apathy.
	
Feasibility measures will include recruitment rate (per month), randomization success, blind success, retention, and attrition rates.
 
Acceptability will be evaluated using Likert scale (from 0 [strongly disagree] to 10

	[strongly agree]) to answer ten affirmatives regarding the use of home-based tDCS. Safety will be assessed with a questionnaire about side effects that include itching, burning, headache, fatigue, and dizziness.
Secondary objectives To assess the efficacy of tDCS for ADRD-related symptoms, with a primary focus on apathy.	Neuropsychiatric symptoms and cognitive measures evaluated through validated tools.

Study Design

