Acceptability will be evaluated using the method proposed by Ahn et al. (2019) (29). Participants and/or their caretakers will be asked to apply a Likert scale (from 0 [strongly disagree] to 10 [strongly agree]) to answer ten affirmatives regarding the use of home-based tDCS. For example, question 1: "It was easy to prepare the device and accessories", question 7: "I felt confident using the device." Overall acceptability across groups will be evaluated by descriptive measures of satisfaction ratings. GLM will model participant satisfaction ratings as a function of treatment group (active vs. sham tDCS). We expect that participant satisfaction ratings at the end of treatment will demonstrate high acceptance of tDCS treatment in the present sample.

Safety will be assessed with a questionnaire about side effects that include itching, burning, headache, fatigue, and dizziness (29). Descriptive statistics will describe raw frequencies of AEs and side effects. Treatment group differences in AEs and side effects will be evaluated via Chi-square and Fisher's exact test of contingency tables. We expect that adverse events and side effects will be rare, and any that may occur will be mild.

The primary clinical outcome measure will be change on the Apathy Evaluation Scale score (42), the best-validated scale for measuring apathy in AD, which consists of 18 items phrased as questions that are to be answered by the caregiver on a four-point Likert scale, with higher scores indicating greater severity of apathy. Apathy will be

assessed at baseline, during treatment (weeks 2, 4 and 6) and 6 weeks post-treatment. Our hypothesis is that active tDCS group will demonstrate lower apathy scores at the end of treatment relative to sham tDCS. GLM will evaluate residual change by modeling apathy at the end of treatment as a function of treatment group, controlling for apathy at the beginning of treatment. This analysis is a regression-based analogue to ANCOVA that permits non-normally distributed outcome distributions. Follow-up analyses will evaluate change over time across groups via GLM with multilevel components (GLMM) as well as cross-sectional analyses within each measurement time point via GLM.

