Potential Benefits to Research Participants. If our hypothesis is correct, subjects in the active arm of the study might benefit from the study participation. Importantly, the results will be relevant to the field of AD and neuromodulation.

Significance

Our proposal will address a frequent and sometimes overlooked clinical problem in patients with ADRD, i.e. apathy. The proposal can advance the field of non-pharmacological strategies for NPS, also presenting a great potential for clinical translation. Home-based intervention with real-time monitoring through a secure conferencing platform is a new modality for improving symptom management in ADRD. Moreover, home-based, remotely supervised tDCS has advantages over clinic-based sessions, considering the time and cost associated with attending multiple sessions over several days. Caregivers will be trained at the in-person baseline visit, and all the tDCS sessions will be remotely supervised via secure videoconferencing software by trained research staff for the entire duration of each session to ensure the use of proper technique and to monitor any adverse events.

Costs and Compensations

Subjects will not be charged for tests, procedures or other costs incurred solely for the purposes of this research. Patients will receive a voucher of US 50.00 for their time dedicated to each evaluation (total number of assessments = 5).

This project was approved to receive financial support from Texas Alzheimer's Research and Care Consortium (TARCC) 2020 Grant Program.

Publication Plan

This study will represent an original contribution to the areas of non-pharmacological approaches for NPS in ADRD and neuromodulation in ADRD, also fostering home-based interventions. More importantly, we expect to have enough evidence on the feasibility, acceptability, safety and efficacy of tDCS for apathy in AD so we can adjust and/or expand the protocol, ultimately, aiming its translation into the clinical practice. This project, if granted, will also strength emerging clinical research groups at UTHealth working with novel technologies that can be applied to ADRD and other neuropsychiatric conditions.

References

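### The side-effects questionnaire has no baseline administration, so the raw safety rates will include headache, fatigue and dizziness present before stimulation, and the active-sham comparison is diluted

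*Combined protocol and SAP*

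**What the plan says.** The primary objective is "To assess feasibility, acceptability, and safety of providing tDCS to ADRD patients with apathy". The safety instrument is named in the Objectives table and again in Study Procedures: "Safety will be assessed with a questionnaire about side effects that include itching, burning, headache, fatigue, and dizziness".

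In Table 1 the row "Side effects questionnaire" is marked at weeks 2, 4, 6 and 12, and the baseline column is empty. The AES, NPI-Q, bDAS, Cornell Scale and MMSE are all marked at baseline.

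The planned analysis has two parts. The first is descriptive: "Descriptive statistics will describe raw frequencies of AEs and side effects". The second is comparative: "Treatment group differences in AEs and side effects will be evaluated via Chi-square and Fisher's exact test of contingency tables". The stated expectation is that events will be rare and mild. There is no treatment-emergent definition, no adjustment for baseline and no attribution rule.

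Other information is collected near this point. Table 1 has a medical history questionnaire at baseline, and Study Procedures adds: "Clinical (health history, use of medication and life habits) and anthropometric data will be collected at the baseline and after the treatment period". Neither is said to cover the five questionnaire symptoms. On supervision, Study Design says that the video link "will ensure the use of proper technique and compliance to the study schedule, also monitoring any adverse events", and Significance says that "all the tDCS sessions will be remotely supervised via secure videoconferencing software by trained research staff for the entire duration of each session".

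**The concern.** Headache, fatigue and dizziness are non-specific. The participants are aged 60 or older with dementia, and no exclusion criterion removes someone who already has one of these symptoms. If such a person reports it at week 2, the plan counts it exactly as it would count an effect of stimulation. The form holds nothing from before the first session to compare with.

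Two results are affected. The first is the per-arm rate, which is what the expectation of rare and mild side effects will be judged on and what a later home-use trial would cite. The second is the active-sham comparison. A background symptom present in both arms hides some stimulation effects, because a participant who already has the symptom cannot be counted a second time. It also adds variance.

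The loss is permanent. A baseline state that was not recorded cannot be recovered once treatment has started.

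**Working it through.** **The plan's own figure.** The documents give no safety rate and no safety power. The only stated power is 80% for the apathy model (N = 40, alpha 0.05, Cohen's f = 0.45). With a noncentral F, noncentrality f² × N = 0.2025 × 40 = 8.1, and 1 and 37 degrees of freedom, power is 79.1%, so the figure reproduces. It has no bearing on safety.

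**Inputs for the illustration.**
- From the documents: 20 per arm (Study Design) and Fisher's exact test (Study Procedures). A two-sided 0.05 level is used here.
- Assumed, because the documents give no rates: one symptom, scored yes or no per participant; new-onset rate 5% on sham and 30% on active; background prevalence b = 30%, range 20% to 40%, equal in both arms by randomisation; background symptoms persist unchanged.

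**Formulas.** For new-onset rate r:
- Raw rate, as planned: b + (1 − b) × r
- New-onset rate over all 20, with a baseline form: (1 − b) × r
- Power: the sum of the two binomial probabilities over all tables for which Fisher's p is at most 0.05.

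**At b = 30%.**
- Raw sham: 0.30 + 0.70 × 0.05 = 0.335. Raw active: 0.30 + 0.70 × 0.30 = 0.51.
- New-onset sham: 0.70 × 0.05 = 0.035. New-onset active: 0.70 × 0.30 = 0.21.

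| Background b | Raw sham / active | Power, raw | New-onset sham / active | Power, new onset |
|---|---|---|---|---|
| 20% | 24% / 44% | 18% | 4% / 24% | 31% |
| 30% | 33.5% / 51% | 12% | 3.5% / 21% | 24% |
| 40% | 43% / 58% | 8% | 3% / 18% | 17% |

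With no background at all, the same onset rates give 45% power.

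**Reading the table.**
1. At b = 30%, the background makes up 0.30 / 0.51 = 59% of the active-arm reports and 0.30 / 0.335 = 90% of the sham reports. The raw rates then say little about stimulation.
2. The expected difference is 51 − 33.5 = 17.5 points on the raw count and 21 − 3.5 = 17.5 points on the new-onset count. The background creates no false difference. It shrinks the 25-point difference in onset rates (30 − 5) to 17.5 points under either count.
3. The baseline form leaves that difference unchanged but removes background noise from it, and power about doubles. It does not bring power back to 45%, because participants who start with the symptom cannot show new onset. Counting worsening may recover some of the rest; that is not modelled here.

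**The case against.** The strongest reply is that this is a randomised, sham-controlled trial. Both arms share the background, and an active-sham comparison is planned. That stands for bias: no false group difference arises in expectation. It does not stand for the per-arm rates, which sham cannot correct, or for the loss of precision.

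A second reply is that other data may serve as a reference. Health history is taken at baseline and after treatment, and the week 12 form falls six weeks after stimulation ends. These are partial at best. The history is not said to record the five symptoms, the week 12 form is a late and imperfect substitute for a pre-treatment state, and the analysis uses neither for this purpose. The questionnaire may itself ask about relation to stimulation, but its wording is not in the documents and the analysis section does not mention it.

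A third reply is that the size rests on assumed rates. That is correct. The illustration also describes a symptom with a background, not itching or burning felt during a session.

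A reader might go further and infer that the forms rely on two-week recall by people with dementia and so miss brief sensations. The documents do not support this. Two weeks is the visit spacing during treatment, not a stated recall period, and no respondent is named. Ethics/Protection of Patient Confidentiality requires a caregiver or relative at assessments and sessions, so that the information is reliable. Staff watch every session throughout and monitor adverse events, and the analysis names adverse events separately from side effects. What is missing is narrower: the respondent, the reference period, and how session observations are recorded and tabulated.

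**Conclusion.** The point holds for the missing baseline and the raw-frequency analysis. As written, the plan will count pre-existing headache, fatigue and dizziness in the per-arm rates of a primary objective, and it weakens the active-sham comparison without biasing it in expectation.

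How much depends on rates that the documents do not give. Under the assumptions shown, a baseline form about doubles power, but power stays low at 20 per arm. The main gain is therefore interpretable per-arm rates. The illustration should not be read as saying that a baseline form restores the power of a population free of background symptoms.

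A reader might also infer that a per-session symptom log should replace the questionnaire. The documents do not make that necessary. Repeated prompting about scalp sensations could also encourage guesses about allocation, and blind success is one of the trial's own primary feasibility measures.

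The change is worth making before enrolment. It does not put the design in question.

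**What to change.** 1. In Table 1, mark the side-effects questionnaire at baseline, to be completed before the first session.
2. In the Safety paragraph of Study Procedures, define a side effect for analysis as a symptom that is new or worse than at baseline. Report and compare those by arm, with raw frequencies alongside. If the form does not grade severity, add a grade so that worsening can be identified.
3. As a supporting step, state who answers the form and over what period, and state how adverse events seen during supervised sessions are recorded and enter the safety tables.

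The cost is one extra five-item form at a visit that already takes place, plus a few sentences of text. The downside is that a symptom present at baseline counts only if it worsens, so a stimulation effect that leaves it at the same grade will not appear in the main count. Keeping the raw frequencies alongside lets a reader see this.
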